5.1.1 Retesting During Screening or Lead-in Period

Retesting of laboratory parameters and/or other assessments within any single Screening or Lead-in period will be permitted (in addition to any parameters that require a confirmatory value).

Any new result will override the previous result (ie, the most current result prior to first dose) and is the value by which study inclusion will be assessed, as it represents the subject's most current clinical state.

5.2 Study Materials

The site will provide all required materials for the tests performed locally (ie, relevant to clinical laboratory tests). The site will have available a well-calibrated scale for recording body weight, a calibrated sphygmomanometer, and thermometer for temperature. The site will have a validated temperature-controlled refrigerator. The site will provide all materials required for accurate source documentation of study activities including the Lung Cancer Symptom Scale (LCSS) visual analog scale.

BMS will provide a BMS-approved protocol and any amendments or administrative letters (if required). Case report forms (electronic or hard copy) will be provided by BMS. Nivolumab will be supplied by BMS. BMS will also provide the Investigator Brochure (IB).

5.3 Safety Assessments

Only data for the procedures and assessments specified in this protocol should be submitted to BMS on a case report form. Additional procedures and assessments may be performed as part of standard of care; however, data for these assessments should remain in the subject's medical record and should not be provided to BMS unless specifically requested.

Subjects will undergo screening evaluations to determine eligibility as mentioned in [Table 5.1-1](#) prior to first nivolumab dose. Safety, including adverse event monitoring and physical examination, should be monitored continually, and safety assessments are recommended every 2 weeks while receiving nivolumab treatment.

The following assessments should be monitored starting on Cycle 1 Day 1 and will continue as per the schedule in the Time and Events Tables at the specified frequency:

- adverse events continuously throughout the study
- physical examination and physical measurements including weight and ECOG PS
- Complete blood count (CBCs) with differential, including white blood cell (WBC), lymphocyte count, absolute neutrophil count (ANC), hemoglobin, hematocrit, and platelet count. Results to be obtained prior to dosing on infusion days.
- Serum chemistry tests (blood urea nitrogen [BUN] or serum urea level, serum creatinine, sodium, potassium, calcium, chloride, glucose, magnesium, LDH and phosphate). Results to be obtained prior to dosing on infusion days.
- Liver function tests including AST, ALT, total bilirubin, alkaline phosphatase, albumin. Results to be obtained prior to dosing on infusion days.

5.3.1 Imaging Assessment for the Study

Any incidental findings of potential clinical relevance that are not directly associated with the objectives of the protocol should be evaluated and handled by the Study Investigator as per standard medical/clinical judgment.

5.3.2 Vital Signs and Physical Examinations

Vital signs including temperature, blood pressure, heart rate, respiratory rate, oxygen saturation by pulse oximetry at rest (also monitor amount of supplemental oxygen if applicable) within 72 hours of dosing. Obtain prior to dosing and at any time a subject has any new or worsening respiratory symptoms. If a subject shows changes in oxygen saturation or supplemental oxygen requirement, or other pulmonary-related signs (eg, hypoxia, fever) or symptoms (eg, dyspnea, cough) consistent with possible pulmonary adverse events, the subject should be immediately evaluated to rule out pulmonary toxicity, according to the suspected pulmonary toxicity management algorithm contained within the Investigator's Brochure.

5.3.3 Pregnancy Testing

Pregnancy testing must be completed for WOCBP at screening, within 24 hours prior to start of study drug (an extension up to 72 hours prior to start of study drug may be permissible in situations where results cannot be obtained within a 24 hour window), every 4 weeks while receiving the program drugs, and every 4 weeks for 6 months following the end of treatment. Pregnancy testing can be completed more frequently if required by local standards. Pregnancy testing may be performed at home if an in-office visit is otherwise not required. Telephone contacts are required to obtain results for all subjects who perform post-treatment at-home pregnancy testing. Although testing may be performed with home pregnancy testing kits, any positive result must be confirmed by serum pregnancy testing at the program site.

5.4 Efficacy Assessments

Mandatory tumor assessments are to be done at Weeks 9 and 52 (± 5 days), and additional tumor assessments should be performed as required by local standards of care or at the investigator's discretion as discussed in [Table 5.1-2](#) and are recommended every 8-12 weeks until:

- Disease progression per RECIST 1.1 criteria (or discontinuation of study treatment in subjects receiving nivolumab beyond progression)
- Subject lost to follow-up
- Withdrawal of study consent by subject
- End of study

Study evaluations will take place in accordance with [Table 5.1-2](#) and should be performed according to RECIST 1.1 criteria.

High resolution CT with oral or IV contrast or contrast-enhanced MRI are the preferred imaging modalities for assessing radiographic tumor response. If a subject has a known allergy to contrast material, please use local prophylaxis standards to obtain the assessment with contrast if at all possible or use an alternate modality. In cases where contrast is strictly contraindicated, a non-

contrast scan will suffice. Screening assessments, including chest, abdomen, pelvis, brain, and all known or suspected sites of disease, should be performed within 28 days of first dose of study drug. Brain MRI is the preferred imaging method for evaluating CNS metastasis. In addition to chest and abdomen, all known or suspected sites of disease (including CNS) should be assessed at subsequent assessments using the same imaging method and technique. If more than one method is used at screening, then the most accurate method according to RECIST 1.1 should be used when recording data and should again be used for all subsequent assessments. Bone scan, PET scan, or ultrasound is not adequate for assessment of RECIST response. In selected circumstances where such modalities are the sole modality used to assess certain non-target organs, those non-target organs may be evaluated less frequently. For example, bone scans may need to be repeated only when complete response is identified in the target disease or when progression in bone is suspected. Previously treated CNS metastases are not considered measurable lesions for purposes of RECIST determined response.

Tumor measurements should be made by the same investigator or radiologist for each assessment whenever possible. Changes in tumor measurements and tumor responses to guide ongoing study treatment decisions should be assessed by the investigator using RECIST 1.1.

For all subjects, global deterioration of health status requiring discontinuation of treatment without objective evidence of disease progression at that time should be reported as ‘symptomatic deterioration’ in the source data and in the case report form. Every effort should be made to document objective progression (ie, radiographic confirmation) even after discontinuation of treatment.

Survival will be followed after progression either by direct contact (office visits) or via telephone contact until death, withdrawal of study consent, lost to follow-up, or end of study.

[REDACTED]

hospitalization.) Potential drug induced liver injury (DILI) is also considered an important medical event. (See [Section 6.6](#) for the definition of potential DILI.)

Suspected transmission of an infectious agent (eg, pathogenic or nonpathogenic) via the study drug is an SAE.

Although pregnancy, overdose, cancer, and potential drug induced liver injury (DILI) are not always serious by regulatory definition, these events must be handled as SAEs. (See [Section 6.1.1](#) for reporting pregnancies).

Any component of a study endpoint that is considered related to study therapy (eg, death is an endpoint, if death occurred due to anaphylaxis, anaphylaxis must be reported) should be reported as SAE (see [Section 6.1.1](#) for reporting details).

NOTE:

The following hospitalizations are not considered SAEs in BMS clinical studies:

- a visit to the emergency room or other hospital department < 24 hours, that does not result in admission (unless considered an important medical or life-threatening event)
- elective surgery, planned prior to signing consent
- admissions as per protocol for a planned medical/surgical procedure
- routine health assessment requiring admission for baseline/trending of health status (eg, routine colonoscopy)
- medical/surgical admission other than to remedy ill health and planned prior to entry into the study. Appropriate documentation is required in these cases
- admission encountered for another life circumstance that carries no bearing on health status and requires no medical/surgical intervention (eg, lack of housing, economic inadequacy, caregiver respite, family circumstances, administrative reason).
- Admission for administration of anticancer therapy in the absence of any other SAEs (applies to oncology protocols)

6.1.1 Serious Adverse Event Collection and Reporting

Sections 5.6.1 and 5.6.2 in the Investigator Brochure (IB) represent the Reference Safety Information to determine expectedness of serious adverse events for expedited reporting.

Following the subject's written consent to participate in the study, all SAEs, whether related or not related to study drug, must be collected, including those thought to be associated with protocol-specified procedures. All SAEs must be collected that occur after written consent and up to 100 days of discontinuation of dosing.

The investigator should report any SAE that occurs after these time periods and that is believed to be related to study drug or protocol-specified procedure. All SAEs must be reported from the time of informed consent and up to 100 days after discontinuation of dosing (within 30 days of last visit for enrollment/screening failures).

An SAE report should be completed for any event where doubt exists regarding its seriousness.

If the investigator believes that an SAE is not related to study drug, but is potentially related to the conditions of the study (such as withdrawal of previous therapy or a complication of a study procedure), the relationship should be specified in the narrative section of the SAE Report Form.

SAEs, whether related or not related to study drug, and pregnancies must be reported to BMS (or designee) within 24 hours. SAEs must be recorded on the SAE Report Form; pregnancies on a Pregnancy Surveillance Form (electronic or paper forms). The preferred method for SAE data reporting collection is through the eCRF. The paper SAE/pregnancy surveillance forms are only intended as a back-up option when the eCRF system is not functioning. In this case, the paper forms are to be transmitted via email or confirmed facsimile (fax) transmission to:

SAE Email Address: Refer to Contact Information list.

SAE Facsimile Number: Refer to Contact Information list.

For studies capturing SAEs through electronic data capture (EDC), electronic submission is the required method for reporting. The paper forms should be used and submitted immediately, only in the event the electronic system is unavailable for transmission. When paper forms are used, the original paper forms are to remain on site.

SAE Telephone Contact (required for SAE and pregnancy reporting): Refer to Contact Information list.

If only limited information is initially available, follow-up reports are required. (Note: Follow-up SAE reports should include the same investigator term(s) initially reported.)

If an ongoing SAE changes in its intensity or relationship to study drug or if new information becomes available, a follow-up SAE report should be sent within 24 hours to the BMS (or designee) using the same procedure used for transmitting the initial SAE report.

All SAEs should be followed to resolution or stabilization.

6.2 Nonserious Adverse Events

A *nonserious adverse event* is an AE not classified as serious.

6.2.1 Nonserious Adverse Event Collection and Reporting

The collection of nonserious AE information should begin at initiation of study drug. All nonserious adverse events (not only those deemed to be treatment-related) should be collected continuously during the treatment period and for a minimum of 100 days following the last dose of study treatment.

Nonserious AEs should be followed to resolution or stabilization, or reported as SAEs if they become serious (see [Section 6.1.1](#)). Follow-up is also required for nonserious AEs that cause interruption or discontinuation of study drug and for those present at the end of study treatment as appropriate. All identified nonserious AEs must be recorded and described on the nonserious AE page of the CRF (paper or electronic).

Completion of supplemental CRFs may be requested for AEs and/or laboratory abnormalities that are reported/identified during the course of the study.

6.3 Laboratory Test Result Abnormalities

The following laboratory test result abnormalities should be captured on the nonserious AE CRF page or SAE Report Form (paper or electronic) as appropriate:

- Any laboratory test result that is clinically significant or meets the definition of an SAE
- Any laboratory test result abnormality that required the subject to have study drug discontinued or interrupted
- Any laboratory test result abnormality that required the subject to receive specific corrective therapy.

It is expected that wherever possible, the clinical rather than laboratory term would be used by the reporting investigator (eg, anemia versus low hemoglobin value).

6.4 Pregnancy

If, following initiation of the study drug, it is subsequently discovered that a study subject is pregnant or may have been pregnant at the time of study exposure, including during at least 5 half lives after product administration, the investigator must immediately notify the BMS Medical Monitor/designee of this event and complete and forward a Pregnancy Surveillance Form to BMS Designee within 24 hours and in accordance with SAE reporting procedures described in [Section 6.1.1](#).

In most cases, the study drug will be permanently discontinued in an appropriate manner (eg, dose tapering if necessary for subject safety).

In the rare event that the benefit of continuing study drug is thought to outweigh the risk, after consultation with BMS, the pregnant subject may continue study drug after a thorough discussion of benefits and risk with the subject.

Protocol-required procedures for study discontinuation and follow-up must be performed on the subject unless contraindicated by pregnancy (eg, x-ray studies). Other appropriate pregnancy follow-up procedures should be considered if indicated.

The investigator must immediately notify the BMS (or designee) Medical Monitor of this event and complete and forward a Pregnancy Surveillance Form to BMS (or designee) within 24 hours and in accordance with SAE reporting procedures described in Section 6.1.1.

Follow-up information regarding the course of the pregnancy, including perinatal and neonatal outcome and, where applicable, offspring information must be reported on the Pregnancy Surveillance Form.

Any pregnancy that occurs in a female partner of a male study participant should be reported to BMS. Information on this pregnancy will be collected on the Pregnancy Surveillance Form.

6.5 Overdose

An overdose is defined as the accidental or intentional administration of any dose of a product that is considered both excessive and medically important. All occurrences of overdose must be reported as an SAE. (See [Section 6.1.1](#) for reporting details.)

6.6 Potential Drug Induced Liver Injury (DILI)

Wherever possible, timely confirmation of initial liver-related laboratory abnormalities should occur prior to the reporting of a potential DILI event. All occurrences of potential DILIs meeting the defined criteria must be reported as SAEs (see [Section 6.1.1](#) for reporting details).

Potential drug induced liver injury is defined as:

- 1) AT (ALT or AST) elevation > 3 times upper limit of normal (ULN)
AND
- 2) Total bilirubin > 2 times ULN, without initial findings of cholestasis (elevated serum alkaline phosphatase),
AND
- 3) No other immediately apparent possible causes of AT elevation and hyperbilirubinemia, including, but not limited to, viral hepatitis, pre-existing chronic or acute liver disease, or the administration of other drug(s) known to be hepatotoxic.

6.7 Other Safety Considerations

Any significant worsening noted during interim or final physical examinations, electrocardiogram, x-ray filming, any other potential safety assessment required or not required by protocol should also be recorded as a nonserious or serious AE, as appropriate, and reported accordingly.

7 DATA MONITORING COMMITTEE AND OTHER EXTERNAL COMMITTEES

The Scientific Steering Committee (SSC) will closely review the safety data throughout the study to provide guidance and scientific expertise on the risk/benefit ratio in general and for the separate prospective subgroups following a predefined Safety Management Plan respecting the data for rate and frequency of Grade 3 and 4 select adverse events (estimated < 25%) and QoL (patient-reported outcomes).

8 STATISTICAL CONSIDERATIONS

8.1 Sample Size Determination

The total sample size for this study is based on logistical considerations. Nevertheless, certain statistical properties of the projected sample size are indicated below.

A total of 950 subjects who are evaluated based on the ECOG PS will be enrolled, and a minimum of 11% (95 subjects) should present with PS2. In addition, a minimum of 40% of patients should be enrolled as second-line, and a minimum of 40% of patients should be enrolled as third-line. With a 15% screen failure rate, a total of approximately 800 subjects will be treated. With $n = 800$

subjects, about 4 subjects will experience a rare adverse event with 0.5% true cumulative event rate within 95% confidence interval (CI) (0.1%-1.3%). Approximately 2 subjects with events and a 95% CI of 0.1%-0.9% for the assumed true event rate of 0.3% are projected. In addition, with 800 subjects, the probability of observing at least one rare event (with 0.25% true rate) is 91.0%.

The 95% CI is calculated using the Clopper-Pearson method in PASS12.

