Mandatory tumor assessments are to be completed at Weeks 9 and 52 (±5 days). Additional tumor assessments should be performed as required by local standards of care or at the investigator’s discretion as discussed in the Time and Events Schedule and are recommended every 8-12 weeks until disease progression per RECIST 1.1 criteria (or discontinuation of study treatment in subjects receiving nivolumab beyond progression), subject lost to follow up, withdrawal of study consent by subject, or end of study. Overall survival will be collected for at least 3 years and up to 5 years from the first dose of study therapy, as indicated in the assessment tables.

Statistical Considerations:

Sample Size: A total of 950 subjects who are evaluated based on the ECOG PS will be enrolled; Subgroup 1 will enroll subjects with PS 0-1 (n ~ 855), and Subgroup 2 will enroll subjects with PS 2 (n ~ 95). The screen failure rate is anticipated to be 15%, which results to approximately 719 and 81 treated subjects in Subgroup 1 and Subgroup 2, respectively.

With n=800 subjects, about 4 subjects will experience a rare adverse event with 0.5% true cumulative event rate with a rate estimate within a 95% confidence interval (CI) (0.1%-1.3%). Approximately 2 subjects with events and a 95% CI of (0.1%-0.9%) for assumed true event rate of 0.25% are projected.

The 95% CI is calculated using the Clopper-Pearson method in PASS12.

Endpoints: The primary endpoint is the incidence of high-grade (CTCAE v4.0 Grades 3-4), treatment-related, select adverse events

The secondary endpoints include:

- Incidence of high grade (Grades 3-4) select adverse events
- Median time to onset and median time to resolution (Grades 3-4) of select adverse events
- OS
- ORR

Analyses: The analysis of primary, secondary (excluding objective response rate), and exploratory endpoints will be reported for the full safety analysis set and subgroups based on ECOG PS. ORR will be reported for the response evaluable analysis set and by PS subgroups and randomized cohorts

Analysis of Primary Endpoints

The number and percentage of subjects who report high-grade (Grades 3-4), treatment-related, select adverse events will be summarized for all treated subjects and by subgroups. Treatment-related, select adverse events will be tabulated using worst grade per NCI CTCAE V4.0 criteria by system organ class (SOC) and Medical Dictionary for Regulatory Affairs (MedDRA) preferred terms.

Analysis of Secondary Endpoints

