5 SAMPLE SIZE AND POWER

The total sample size for this study is based on logistical considerations. Nevertheless, certain statistical properties of the projected sample size are indicated below.

A total of 950 subjects who are evaluated based on the ECOG PS will be enrolled, and a minimum of 30% (285 subjects) should present with PS2. In addition, a minimum of 40% of patients should be enrolled as second-line, and a minimum of 40% of patients should be enrolled as third-line. With a 15% screen failure rate, a total of approximately 800 subjects will be treated. If the true cumulative incidence rate is 0.5 then with $n = 800$ subjects, about 3 subjects will experience a rare adverse event (with a 95% confidence interval (CI) of 0.1%-1.3%) for the cumulative incidence rate. If the assumed true event rate is 0.3% then approximately 3 subjects will experience events with a 95% CI of 0.1%-0.8% for the assumed true event rate. In addition, with 800 subjects, the probability of observing at least one rare event (with 0.3% true rate) is 91.0%.

The 95% CI is calculated using the Clopper-Pearson method.

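### Protocol 8.1 claims a 91.0% chance of seeing a 0.25% event among 800 subjects; the correct value is 86.5%, and several companion figures in the protocol and SAP also need correcting

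*Protocol*

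**What the plan says.** Protocol 8.1 says that the sample size was set on logistical grounds and then offers some statistical properties of about 800 treated subjects.

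- **Detection probability, Protocol 8.1:** "with 800 subjects, the probability of observing at least one rare event (with 0.25% true rate) is 91.0"%.
- **Detection probability, SAP 5:** "the probability of observing at least one rare event (with 0.3% true rate) is 91.0"%.
- **Low-rate projection, Protocol 8.1:** "Approximately 2 subjects with events and a 95% CI of 0.1%-0.9% for the assumed true event rate of 0.3% are projected".
- **Low-rate projection, Protocol Synopsis:** "Approximately 2 subjects with events and a 95% CI of (0.1%-0.9%) for assumed true event rate of 0.25% are projected".
- **Low-rate projection, SAP 5:** "If the assumed true event rate is 0.3% then approximately 3 subjects will experience events with a 95% CI of 0.1%-0.8"%.
- **Rate of 0.5%:** Protocol 8.1 projects about 4 events with an interval of 0.1% to 1.3%. SAP 5 writes "If the true cumulative incidence rate is 0.5 then" and goes on to say that "about 3 subjects will experience a rare adverse event (with a 95% confidence interval (CI) of 0.1%-1.3"%.
- **Interval method:** both documents name Clopper-Pearson.
- **PS 2 share, Protocol 8.1:** "a minimum of 11% (95 subjects) should present with PS2", out of 950 enrolled. The Synopsis gives 855 and 95 enrolled, and 719 and 81 treated, for PS 0-1 and PS 2. Protocol 3.3.1 makes 95 enrolled and 81 treated a minimum for PS 2.
- **PS 2 share, SAP:** section 5 has a minimum of 30% (285 subjects). Table 2.1-1 has 565 and 242.

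**The concern.** The same 91.0% is attached to 0.25% in the protocol and to 0.3% in the SAP. With 800 subjects in both, it cannot be right for both rates. The same count and interval (2 events, 0.1% to 0.9%) are likewise attached to 0.25% in the Synopsis and to 0.3% in section 8.1, and within 8.1 two consecutive sentences switch from one rate to the other.

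Because the sample size rests on logistics, these lines are the only quantitative support the plan gives for treating 800 subjects, in a study whose primary endpoint is the incidence of adverse events. A reader who relies on 8.1 will think the study less likely to miss a 0.25% event than it is.

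The two documents also describe PS 2 subgroups of very different size, and Protocol section 7 has the steering committee review the subgroups separately.

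**Working it through.** **Inputs.** n = 800 treated; rates 0.25%, 0.3% and 0.5%; two-sided 95% Clopper-Pearson intervals (Protocol Synopsis and 8.1; SAP 5). Enrolled and treated subgroup sizes come from the Protocol Synopsis, 3.3.1 and 8.1, and from SAP 5 and Table 2.1-1.

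**Detection probability.** P(at least one event) = 1 − (1 − p)^n.

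- p = 0.3%: 1 − 0.997^800 = 0.9096, or 91.0%. This reproduces the SAP figure.
- p = 0.25%: 1 − 0.9975^800 = 0.8650, or 86.5%. Protocol 8.1 prints 91.0%.
- Chance of no event at 0.25%: 13.5%, against 100 − 91.0 = 9.0% implied.
- Rounding of n does not explain it: n = 807 gives 86.7% and n = 808 gives 86.8%. The enrolled number, 950, gives 90.7%, but the sentence says 800. Reaching 91.0% at 0.25% needs ln(0.09)/ln(0.9975), about 962 subjects.

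**Expected events.** 800 × 0.0025 = 2.0; 800 × 0.003 = 2.4; 800 × 0.005 = 4.0.

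**Intervals.** For x events, the lower limit is the 0.025 quantile of Beta(x, n − x + 1) and the upper limit the 0.975 quantile of Beta(x + 1, n − x).

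| Events / 800 | Clopper-Pearson 95% | Printed |
|---|---|---|
| 4 | 0.14% to 1.28% | 0.1% to 1.3% (protocol, 4 events at 0.5%): reproduces. SAP: same interval, but with 3 events |
| 2 | 0.03% to 0.90% | 0.1% to 0.9% (protocol): upper limit right, lower limit wrong |
| 3 | 0.08% to 1.09% | 0.1% to 0.8% (SAP, 3 events at 0.3%): matches neither 3/800 nor 2/800 |

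Other methods come closer for 2/800: Wilson gives 0.07% to 0.91% and Jeffreys 0.05% to 0.80%. Neither is the method the documents name.

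**SAP at 0.5%.** The count should be 4, and the SAP's own interval is the one for 4/800.

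**PS 2 share.** 95/950 = 10.0%. A true 11% would be 0.11 × 950 = 104.5 subjects.

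**Subgroup sizes.**

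- SAP: 285 × 0.85 = 242 and (950 − 285) × 0.85 = 665 × 0.85 = 565. These follow from the 30% minimum. They sum to 807, against the 800 stated in the same table.
- Protocol: 95 × 0.85 = 81, but 855 × 0.85 = 727, not 719. The figure 719 equals 800 − 81 and implies 1 − 719/855 = 15.9% screen failure.
- 242/81 is about 3.

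**Timing.** The SAP says it is based on Revised Protocol 03, and its last listed version is 2.0 of 18 July 2016. Amendment 04, which adjusted the subgroup numbers, is dated 26-Oct-2016.

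**What the subgroup difference means for precision.** The documents give no PS 2 event rate, so I assume observed rates of about 5% to 25%; 25% is the bound for Grade 3 and 4 select events in Protocol section 7.

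| Treated PS 2 | About 5% | About 25% |
|---|---|---|
| 81 | 4/81: 1.4% to 12.2%, half-width 5.4 points | 20/81: 15.8% to 35.5%, half-width 9.9 points |
| 242 | 12/242: 2.6% to 8.5%, half-width 3.0 points | 60/242: 19.5% to 30.7%, half-width 5.6 points |

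**The case against.** The strongest reply is that none of this drives the study. The sample size is declared logistical, no test or stopping rule uses these lines, and the only rate the documents give for Grade 3 and 4 select events is a bound of 25%, far from 0.25%. On that view, a 4.5-point slip in an illustrative probability is an erratum. The facts are right and they limit the weight of the point, but they do not make the figure correct.

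Some items are indeed clerical. The gaps of 719 against 727 and 807 against 800 are about 1% and sit beside words such as approximately. The missing percent sign in SAP 5 misleads nobody, since the interval next to it is in percent. The 11% may have come from 95/855 = 11.1%, and the count of 95 is clear. I give these little weight.

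The SAP subgroup sizes are a version lag, not an arithmetic error: the SAP names the protocol version it follows and could not anticipate a later amendment. The timing is also not fully settled. The protocol's document history shows that Administrative Letter 02 (14-Aug-2015) had already adjusted these numbers, before the first SAP version of 4 Sept 2015, so the SAP's figures may have been out of date earlier. Either way, the current texts disagree.

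Finally, 81 is a minimum, so more PS 2 subjects could be treated, and the precision comparison rests on assumed rates.

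**Conclusion.** The concern holds. At a 0.25% true rate with 800 subjects, the probability of seeing at least one event is 86.5%, not 91.0%, and the chance of missing it is understated by 4.5 points (9.0% against 13.5%). This is exact binomial arithmetic on the document's own inputs, and it assumes only independent subjects with a common rate.

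Also wrong as printed are the lower limit for 2/800 in the protocol, the count at 0.5% and the interval at 0.3% in SAP 5, and the 11%. The protocol's 0.5% line, the Synopsis count of 2 events with its 0.9% upper limit at 0.25%, and the SAP's 91.0% at 0.3% all reproduce and can stand.

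The SAP's PS 2 subgroup is about three times the protocol's current minimum and should be aligned. No analysis or sample size changes. This should be corrected because these lines are the plan's only statistical description of what 800 subjects can show.

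**What to change.** **Protocol Synopsis and 8.1.** Use one low rate throughout.

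- If 0.25%: 2 expected events, interval for 2/800 of 0.03% to 0.90%, detection probability 86.5%. This is the tidier choice, because the count is whole and the Synopsis already uses that rate.
- If 0.3%: 2.4 expected events and detection probability 91.0%. Any interval shown has to be for a whole count, so label the 2/800 interval (0.03% to 0.90%) as illustrative.

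Replace 11% with 10% beside the 95 subjects. Reconcile enrolled and treated sizes: either 855 enrolled gives about 727 treated at 15% screen failure (727 + 81 = 808), or say that 719 is 800 − 81.

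**SAP 5.** State 4 events at 0.5%, with the percent sign and the interval of 0.1% to 1.3%. Carry the same low-rate line as the protocol.

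**SAP 5 and Table 2.1-1.** After the protocol figures are reconciled, replace 30%, 285, 242 and 565 with the current subgroup sizes, and update the protocol version on which the SAP says it is based. A precision statement for PS 2 at 81 treated would be useful but is optional; if added, it should label its assumed rate.

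**Cost.** Text corrections only, with no added patients and no change to any analysis. If 0.25% is kept, the stated detection probability falls from 91.0% to 86.5%.
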